Official Study Title: Effects of Boccia Exercises on Upper Extremity Muscle Thickness and Grip Strength in Hemiparetic Individuals

NCT Number: NCT ID not yet assigned

Document Type: Study Protocol with Statistical Analysis Plan (SAP)

Document Date: 15 November 2025

Principal Investigator: [name]

Institution: Bayburt University

Study Protocol with Statistical Analysis Plan: Effects of Boccia Exercises on Upper Extremity Muscle Thickness and Grip Strength in Hemiparetic Individuals

Study Design

This is a randomized controlled trial (RCT) with a true experimental pretest-posttest control group design. The study aims to examine the effects of an 8-week Boccia exercise program on upper extremity muscle architecture and grip strength in hemiparetic individuals, in addition to their ongoing rehabilitation program.

- Duration: 8 weeks
- Frequency: 3 sessions per week for both physical therapy and Boccia exercises
- Groups:
 - Experimental Group: Physical therapy + Boccia exercises
 - Control Group: Physical therapy only

To standardize measurements, participants refrained from physical therapy sessions for 48 hours prior to assessment and avoided caffeine and alcohol for 24 hours. Two independent evaluators ensured blinding: Evaluator 1 conducted all measurements, while Evaluator 2 administered the Boccia program.

Participants

- Population: Adults aged 18–75 with hemiparesis post-stroke (6–24 months post-event)
- Inclusion Criteria: Clinically stable, able to follow instructions, attend sessions, and provide consent
- Exclusion Criteria: Severe spasticity, major comorbidities, recent upper extremity surgery, severe cognitive impairment, or participation in other trials

Interventions

Boccia Exercise Group (Experimental)

- Weeks 1–2: Flexibility training and introduction to basic Boccia throwing techniques
- Weeks 3–8: Physical therapy sessions plus one Boccia session per day; progressive complexity in throwing techniques, including tactical training and match play
- Supervision: Each session led by a physiotherapist and Boccia coach
- Session Duration: ~1 hour

Control Group

- Conventional physical therapy only: strengthening, range of motion, motor retraining, and functional exercises matched for duration and frequency

Outcome Measures

Primary Outcome

Grip Strength

- Measured with a Jamar Hydraulic Hand Dynamometer
- Participant seated with elbow at 90°, forearm neutral, wrist 0–30° extension
- Three trials per assessment; highest value recorded (kg)

- Assessment Timepoints: Baseline and post-intervention (8 weeks)

Secondary Outcome

Upper Extremity Muscle Thickness

- Measured using B-mode ultrasonography (SonoHealth dual-sector + linear probe)
- Muscles assessed: biceps brachii, brachialis, triceps brachii, anterior deltoid, forearm and hand muscles
- Measurement points standardized using anatomical landmarks
- Three images per site; average used for analysis (mm)
- Assessment Timepoints: Baseline and post-intervention

Statistical Analysis

- Conducted with IBM SPSS v21.0
- Normality tested with Shapiro-Wilk
- Categorical variables compared with Chi-square or Fisher's exact test
- Changes over time and between groups evaluated with two-way repeated measures ANOVA (2 × 2)
- Post hoc analyses applied if significant Time × Group interaction detected
- Significance Level: $p \leq 0.05$

Randomization & Blinding

- Participants randomly allocated to experimental or control groups
- Evaluator 1 blinded to group allocation
- Evaluator 2 administered Boccia exercises exclusively
- Participants aware of their intervention (cannot be blinded)

Safety & Monitoring

- All participants monitored for adverse events
- Physiotherapist present during all sessions to minimize risk of injury
- Session adherence and tolerance recorded

Ethics & Data Management

- Informed consent obtained from all participants
- Collected data anonymized for analysis
- Data stored securely and used solely for research purposes

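### Does leaving the tested hand unnamed in the primary grip-strength outcome put the 5% significance level at risk?

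*Combined protocol and SAP*

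**What the plan says.** The Primary Outcome entry under Outcome Measures is a short list. The instrument is given ("Measured with a Jamar Hydraulic Hand Dynamometer"), then the position ("Participant seated with elbow at 90°, forearm neutral, wrist 0–30° extension"), then the summary ("Three trials per assessment; highest value recorded (kg"), then the two visits, baseline and 8 weeks. No line names the paretic, non-paretic, dominant or throwing hand, and none says how two hands would be combined.

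Statistical Analysis states "Changes over time and between groups evaluated with two-way repeated measures ANOVA" in a 2 × 2 layout. Post hoc work depends on the Time × Group interaction, and the threshold is p ≤ 0.05. There is no hand factor and no multiplicity rule. Randomization & Blinding adds "Evaluator 1 blinded to group allocation". The body side is also unstated for the secondary outcome, muscle thickness.

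**The concern.** Every participant has one impaired side, so a gain in the paretic hand and a gain in the other hand are different conclusions. The plan does not exclude measuring both. With two candidate endpoints, one 5% threshold and no rule linking them, an analyst could look at both and call the better one primary. A blinded evaluator protects the measurement but not that later choice.

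The document also describes assessment in the past tense ("participants refrained from physical therapy sessions for 48 hours prior to assessment") and carries the header "NCT ID not yet assigned". This raises the question of whether data existed before the hand was settled. If the hand were chosen on results, the false-positive rate would exceed 5%, and an estimate picked for its size would be too large.

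**Working it through.** **Inputs.** From the documents: threshold 0.05, two groups, two visits, one recorded maximum per assessment, factors time and group only. Not in the documents: the correlation ρ between the two hands' test statistics (assumed, 0 to 0.9) and the sample size (10, 15 and 30 per arm assumed, only to check the formulas by simulation with 100,000 null trials per setting). The Time × Group interaction is taken as the deciding test. The plan implies this by making post hoc work depend on it, but does not say so outright.

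**Step 1: the plan's own figure.** With two visits, the interaction F test is the square of a two-sample t-test on change (week 8 minus baseline). With one value per participant per visit there is one test, and its error rate is 0.05. Simulation gives 0.049 to 0.051.

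**Step 2: one fixed rule for combining hands.** A single mean or maximum over the two hands still gives one number per participant and one test. Simulation gives 0.0485 to 0.0513. So the 5% level does not need one particular hand; it needs one definition settled before the comparison.

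**Step 3: the adverse case.** Suppose both hands are measured and either may count.

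- Two-sided rate = 1 − P(|Z₁| < 1.96 and |Z₂| < 1.96). At ρ = 0 this is 1 − 0.95² = 0.0975.
- Rate of false claims favouring Boccia = 1 − P(Z₁ < 1.96 and Z₂ < 1.96). At ρ = 0 this is 1 − 0.975² = 0.0494.
- Inflation from reporting the larger of two estimates with equal true effects and equal standard errors = √((1 − ρ)/π) standard errors. At ρ = 0.5 this is √(0.5/π) = 0.399.

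| ρ (assumed) | Two-sided | Favouring Boccia | Inflation (SE) |
|---|---|---|---|
| 0 | 9.75% | 4.94% | 0.56 |
| 0.5 | 9.07% | 4.54% | 0.40 |
| 0.8 | 7.81% | 3.90% | 0.25 |
| 0.9 | 7.04% | 3.52% | 0.18 |
| one fixed definition | 5.00% | 2.50% | 0 |

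Simulated t-tests agree for the two-sided rate: 0.098 to 0.099 at ρ = 0, 0.090 to 0.092 at 0.5, and 0.070 to 0.072 at 0.9.

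**Step 4: which case do the documents describe?** Step 3 needs two things: both hands measured, and the choice made after group results are seen. Neither is stated. The outcome entry gives three attempts and one retained value per assessment, and the model has cells for time and group only. Together these most naturally describe one grip value per participant per visit, which is Step 1. The past tense is weak evidence of anything: the document also uses it for consent and anonymisation, so it may be only style. The missing registry number says nothing about the hand.

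**The case for a change.** The strongest case for the concern is that the omission is complete and nothing elsewhere repairs it. The intervention text does not say which arm throws, and muscle thickness names muscles but no side. If the paretic hand is obviously meant, stating it would take one line. If both hands were tested, the retained maximum is itself ambiguous: within a hand it is one thing, but across hands it would mostly report the unimpaired side. If side was not recorded, the information may be lost.

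The ambiguity stands: the plan alone does not tell a reader which hand the primary result describes. The conditional arithmetic stands too. What does not stand is the step from ambiguity to an error rate above 5%. That step adds a second measured hand and a choice driven by results, and the documents show neither. Even the maximum across hands, used as a single rule, changes the question answered but keeps the 5% level.

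**Conclusion.** The hand is missing from the primary outcome, and this is a gap rather than an error. No rule in the plan gives a wrong result because of it. On the natural reading, one value per participant per visit, the error rate is 5% and the excess is zero. The same holds under any single rule for combining hands settled in advance. An excess of 2.0 to 4.75 percentage points (7.04 − 5 to 9.75 − 5) arises only if both hands were measured and either could count, with ρ assumed between 0.9 and 0.

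An analyst of a pretest-posttest trial in hemiparesis would fix one hand and use it at both visits as a matter of course. Any intelligible report of grip strength here has to say which hand it was. Amending the plan would only record a choice; it would not replace a faulty method with a better one. No change follows. This rests on the hand or combining rule being settled before groups are compared, and on the Time × Group interaction being the deciding test.

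### The 2 × 2 repeated-measures ANOVA gives a valid interaction test, but baseline-adjusted ANCOVA would usually be more precise, and the plan does not designate the efficacy contrast

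*Combined protocol and SAP*

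**What the plan says.** The Study Design section describes a randomised trial with a "true experimental pretest-posttest control group design", and Randomization & Blinding repeats that "Participants randomly allocated to experimental or control groups". The primary outcome, grip strength in kg, is measured twice: "Assessment Timepoints: Baseline and post-intervention (8 weeks"). Muscle thickness, the secondary outcome, is also measured before and after the intervention.

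For the analysis, the Statistical Analysis section gives "Changes over time and between groups evaluated with two-way repeated measures ANOVA (2 × 2") and then "Post hoc analyses applied if significant Time × Group interaction detected", at a significance level of 0.05. It mentions no baseline covariate, no effect estimate and no confidence interval. It does not say which of the three ANOVA tests (Time, Group, interaction) supports the efficacy claim, and it does not define the post hoc comparisons.

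**The concern.** Two things are at stake.

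**Precision.** With two time points, the interaction test compares mean change between arms. That amounts to assuming that a patient who starts 1 kg higher is expected to finish 1 kg higher. When the true slope is below 1, the usual case with similar SDs at both times, change scores carry avoidable noise. The baseline values needed to remove it are already being collected.

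**Which test counts.** Of the three tests, only the interaction isolates the treatment effect. The Time effect shows whether patients changed overall, and both arms receive physical therapy, so a shared gain is plausible. The Group effect averages the pre-treatment value with the 8-week value, so it carries only half the treatment effect. A report could therefore rest on a result that is not evidence of efficacy, or on within-arm comparisons made as post hoc tests.

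**Working it through.** **Inputs from the documents:** two randomised arms, two time points, alpha 0.05, no covariate. **Assumed, because the documents give none:** 1:1 allocation, n per arm, correlation r between baseline and 8 weeks, SDs, effect size, normal data, complete follow-up. The plan has no figure of its own to reproduce.

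**1. Equivalence and validity.** On one simulated data set (15 per arm) the interaction F was 9.9594 and the squared t on change scores was 9.9594. In simulations with no treatment effect, the interaction test rejected in 4.7% to 5.1% of trials for 10 to 30 per arm and r from 0.5 to 0.9. The planned test is sound.

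**2. Precision, equal SDs.** In units of SD²:

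- Change score: (2/n) × 2(1 − r)
- ANCOVA: (2/n) × (1 − r²) × [1 + 1/(2n − 4)], where the bracket is the cost of estimating the slope
- Ratio ANCOVA/change: (1 + r)/2 × [1 + 1/(2n − 4)]

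For 20 per arm the bracket is 1 + 1/36 = 1.028. At r = 0.5 the ratio is 0.75 × 1.028 = 0.77. Setting the ratio to 1 gives the break-even correlation (2n − 5)/(2n − 3).

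| n per arm | r = 0.5 | r = 0.7 | r = 0.9 | Gain ends at r |
|---|---|---|---|---|
| 10 | 0.80 | 0.90 | 1.01 | 15/17 = 0.88 |
| 20 | 0.77 | 0.87 | 0.98 | 35/37 = 0.946 |
| 30 | 0.76 | 0.87 | 0.97 | 55/57 = 0.965 |

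At 20 per arm the 95% CI is narrower by 1 − √ratio: about 12%, 6.5% and 1%.

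**3. Power, 20 per arm, 0.6 SD effect.** Planned test: noncentral t with 38 df. ANCOVA: noncentral t with 37 df, averaged over chance baseline imbalance.

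| r | Planned | ANCOVA |
|---|---|---|
| 0.5 | 46% | 56% |
| 0.7 | 67% | 72% |
| 0.9 | 98.5% | 98.7% |

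**4. Unequal SDs.** With s = 8-week SD / baseline SD, the ratio is s²(1 − r²)/(1 + s² − 2rs) × [1 + 1/(2n − 4)]. At 20 per arm:

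| s | r = 0.5 | r = 0.7 | r = 0.8 | r = 0.9 |
|---|---|---|---|---|
| 0.8 | 0.59 | 0.65 | 0.66 | 0.62 |
| 1.2 | 0.90 | 0.99 | 1.02 | 1.00 |

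The first factor never exceeds 1, because its denominator minus its numerator is (1 − rs)². With equal arms and a common slope, ANCOVA can therefore lose at most the bracket: 1/36 = 2.8% of variance at 20 per arm.

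**5. Why the choice of contrast matters (15 per arm, r = 0.7, equal SDs).**

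- No treatment effect, shared gain of 0.5 SD: the Time effect has noncentrality 0.5/√(0.6/30) = 3.54 and is significant in about 93% of trials.
- True effect of 0.5 SD: the interaction has noncentrality 0.5/√(0.6 × 2/15) = 1.77 and power of about 40%. The Group effect has 0.25/√(0.85 × 2/15) = 0.74 and power of about 11%.

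**The case against.** The strongest case is that nothing here is wrong: the interaction test is valid, so preferring ANCOVA is a matter of efficiency. The size of the gain cannot be read from the documents. Stable patients across a wide age range, re-measured after 8 weeks with a standardised device, may well have a high r, where little is gained. At 10 per arm, r = 0.9 and a 0.6 SD effect, ANCOVA is marginally worse (80.4% against 81.0% power). A larger 8-week SD also removes the gain, as the 1.02 at s = 1.2 and r = 0.8 shows.

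The 2.8% ceiling depends on equal arms and a common slope, and the plan states no allocation ratio. As an illustration, with 40 and 20 patients, arm slopes of 1.2 and 0.8 and residual variance 0.19, the large-sample ANCOVA variance is about 6% above that of the change score.

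Finally, the interaction is the only effect the plan singles out, so a reader can infer that it is the deciding test. If ambiguity is the problem, one sentence naming it would suffice.

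These points stand as limits. They make "usually" the right word and make the ceiling conditional. They do not remove the case for the change: in the scenarios shown, the variance falls by up to about 40% against a loss of a few per cent. Nor is a gate to undefined post hoc tests a statement of what decides efficacy.

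**Conclusion.** The concern holds, as a recommended improvement and not as an error in the test. The Time × Group test is valid and unbiased. At an assumed 20 per arm with equal SDs, ANCOVA would cut the variance by about 23%, 13% and 2% at r = 0.5, 0.7 and 0.9, with nothing gained from about r = 0.95. These figures rest on assumed sample size, correlation, SDs, effect size, 1:1 allocation and complete data. The point about the contrast needs none of those assumptions: the plan does not explicitly designate the interaction as the efficacy test and commits to no effect estimate or interval.

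**What to change.** Make the primary analysis an ANCOVA of 8-week grip strength (kg) on randomised group, with baseline grip strength as covariate. Report the adjusted between-group difference with its 95% CI and state that it is the sole basis for the efficacy claim. Use the same model for each muscle-thickness site, and report within-arm changes descriptively only.

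If the ANOVA is kept, the minimum is to name the Time × Group interaction as the primary test, report the between-group difference in change with its 95% CI, and state that the Time and Group main effects are not evidence of efficacy.

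The cost is a few lines of SAP wording. The software and data stay the same and no patients are added. ANCOVA uses one more degree of freedom, with the small possible loss of precision described above.

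### The plan names no analysis population, and its 2 × 2 ANOVA compares unadjusted change in grip among completers, which is biased if dropout differs between arms in a way tied to baseline grip and is less precise than a baseline-adjusted analysis

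*Combined protocol and SAP*

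**What the plan says.** Under Outcome Measures, the primary outcome, grip strength, has two assessments: "Assessment Timepoints: Baseline and post-intervention (8 weeks". Under Statistical Analysis, the only method given for comparing the arms on grip is: "Changes over time and between groups evaluated with two-way repeated measures ANOVA (2 × 2". The follow-up rule is "Post hoc analyses applied if significant Time × Group interaction detected", so the interaction carries the treatment effect. The software line reads "Conducted with IBM SPSS v21.0"; neither the procedure within that package nor a missing-value option is named.

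Under Randomization & Blinding: "Participants randomly allocated to experimental or control groups". Under Safety & Monitoring: "Session adherence and tolerance recorded". The adherence record is not tied to any analysis set.

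The document does not name an analysis population, a missing-data method, a sensitivity analysis, a sample size or an expected dropout rate. It does not say whether people who stop attending are still assessed at week 8.

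**The concern.** This is more than an unwritten policy, because the named method brings its own default. With two time points, a participant without a week-8 value has no change score. The standard repeated-measures ANOVA therefore leaves that person out, baseline included, and the randomised comparison becomes a comparison of completers.

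The contrast is also not adjusted for baseline. People who start weak tend to show larger changes than people who start strong, whatever their treatment, because the correlation between the two measurements is below 1. If the completers in the two arms differ in starting grip, part of that tendency enters the treatment effect. Unequal dropout is plausible, since Boccia is added to physical therapy in one arm and participants know their allocation.

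At stake are the direction and precision of the primary grip result. In addition, with no rule written beforehand, exclusions could be decided after the results are seen.

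**Working it through.** **Inputs from the document.** Two arms, two time points, 2 × 2 repeated-measures ANOVA, significance level 0.05. There is no stated figure to reproduce, because the plan gives no sample size, power, SD, correlation or dropout rate. Everything numerical below rests on assumed inputs and shows direction and range only.

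**Step 1: what the interaction tests.** On a simulated data set with 20 per arm, the interaction F equalled t² for the between-arm difference in change scores. The two are the same test.

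**Step 2: bias formula.** Let ρ be the correlation between baseline and week-8 grip, with equal SDs and a treatment effect that does not vary with baseline. Expected change then falls with baseline at slope (ρ − 1), so

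bias = (ρ − 1) × (completers' mean baseline, Boccia minus control).

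The bias is zero if the completers' baselines match, or if ρ = 1.

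**Step 3: size in kg.** Assumed: SD 8 kg, true effect 3 kg, dropout depending only on baseline grip (log-odds 1.0 per SD where it depends at all), 4 million simulated participants per scenario. Bias of the interaction estimate:

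| Dropout pattern | ρ = 0.5 | ρ = 0.7 | ρ = 0.9 |
|---|---|---|---|
| Same dependence on baseline in both arms, about 21% each | +0.01 | +0.01 | -0.01 |
| Depends on baseline in the Boccia arm only, about 20% each | -0.75 | -0.43 | -0.15 |
| Opposite directions by arm, about 21% each | -1.47 | -0.89 | -0.29 |
| Same direction, about 11% control v 21% Boccia | -0.36 | -0.22 | -0.08 |

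Check of row 2 at ρ = 0.5: the completers' baseline difference was +1.48 kg, and (0.5 − 1) × 1.48 = -0.74, against -0.75 simulated. Baseline-adjusted ANCOVA on the same completers was within 0.01 kg of the truth in all four rows.

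**Step 4: size in SD, and type I error.** Assumed: 20–30 per arm, ρ of 0.5–0.7, weaker grip more likely to leave (log-odds 1.5 per SD), no true effect.

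| Dropout, Boccia v control | ANOVA bias (SD) | ANOVA type I error |
|---|---|---|
| 20–30% v 0% | about -0.06 to -0.16 | about 5–8% |
| 20% v 10% | about -0.03 to -0.06 | about 5–6% |
| 20% v 20% | about 0 | about 5% |

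In the first row, ANCOVA bias was about 0 and its error about 5%.

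**Step 5: precision with no dropout.** With SD σ at both times, the residual variance is 2σ²(1 − ρ) for change scores and σ²(1 − ρ²) for ANCOVA. The ratio of standard errors is √(2/(1 + ρ)), which is 1.155 at ρ = 0.5 and 1.085 at ρ = 0.7. Estimating the slope costs ANCOVA a factor √(1 + 1/(2n − 4)) with n per arm:

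- n = 20: √(1 + 1/36) = 1.014, giving ratios of 1.139 and 1.070.
- n = 30: √(1 + 1/56) = 1.009, giving ratios of 1.145 and 1.075.

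The change-score standard error is therefore about 14% larger at ρ = 0.5 and about 7% larger at ρ = 0.7.

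**The case against.** Much of the opposing case stands, and it limits the point in five ways.

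- **Dropout related to baseline is not enough.** A reader might infer that any such dropout biases the result. It does not: the interaction compares changes between arms, and dropout that is alike in both arms cancels when the effect is constant (first row of the kg table, last row of the SD table).
- **Silence is not a decision.** A reader might infer that the plan rejects an analysis as randomised, or orders incomplete cases to be dropped. It says neither. The restriction to completers follows from the standard form of the named method.
- **Unequal dropout is not established.** The Study Design and Interventions sections describe Boccia as added to physical therapy, but the control therapy is also described as equal in length and frequency. Eligibility requires clinical stability and the ability to attend. Dropout of 20–30% in one arm and none in the other is an extreme case. At 20% v 10% with a gradient of 0.5 instead of 1.5, the bias is only -0.01 to -0.03 SD.
- **The excess error is not false benefit.** In the one-arm scenario the bias runs against Boccia. False results favouring Boccia fall from the nominal 2.5% to about 0.5–1.3%, and the excess favours control. Other dropout patterns could reverse the sign, but the documents do not point to one.
- **Leavers who gain nothing are a separate matter.** A reader might argue that a completers' effect then overstates the as-randomised effect by a factor 1/(1 − dropout). That is a property of the assumption about leavers and not a fault of the ANOVA. A mixed model would not remove it, because it treats leavers like similar stayers.

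Baseline adjustment is also not a complete cure. If the effect varies with baseline by 1 kg per SD, ANCOVA and ANOVA on completers both miss the all-randomised average by about +0.18 to +0.19 kg.

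The objection does not remove the missing analysis population, the route to bias when dropout differs by arm, or the loss of precision, which needs no dropout at all.

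**Conclusion.** The point holds in limited form and should be acted on. The plan leaves its analysis population unstated, and its primary method is an unadjusted change-score comparison among people with both grip values. A better method is available with the data already being collected.

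The size of any bias cannot be established from the documents. Under the stated assumptions it ranges from nil (dropout alike in both arms, constant effect), through a few hundredths of an SD with near-nominal error (20% v 10%), to about 0.16 SD with up to about 8% type I error (30% in the Boccia arm only). These figures assume a linear relation between the two measurements with equal SDs, a constant effect, and dropout that depends only on baseline grip. Dropout that depends on the unseen week-8 value was not examined and could also bias the result. The precision loss of about 7–14% assumes a correlation of 0.7–0.5 and 20–30 per arm.

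**What to change.** 1. Make the primary grip analysis a baseline-adjusted comparison of week-8 grip. Use either ANCOVA, or a likelihood-based mixed model with a common baseline mean, which also keeps participants who have a baseline value only (MIXED in SPSS v21). Report the between-arm difference with a 95% confidence interval.
2. State that every randomised participant is analysed in the allocated arm.
3. State that all randomised participants are invited to the week-8 assessment whatever their session attendance.
4. Add one sensitivity analysis that imputes missing Boccia-arm week-8 values from the control arm. This covers leavers who gain nothing, which the mixed model alone does not address.

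The cost is minor SAP rewording, one extra run, and some effort to bring non-attenders back for assessment.
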